Subjects with persistently uncontrolled disease while on adalimumab 80 mg eow should be discontinued from the study.

The Investigator should consider dose escalation in lieu of initiating any rectal therapy such as therapeutic enemas or suppositories during the study. The AbbVie study designated physician identified in Section 6.1.7 should be contacted if there are any questions regarding rectal therapy.

Dose De-Escalation and Re-Escalation

Subjects who have been in remission (PMS \leq 2 with no individual subscore > 1) for at least 8 weeks and for at least 2 consecutive visits may have their dosage decreased from ew to eow prior to Amendment 4 or to the next lower dose after Amendment 4. The investigator should receive prior approval from the medical monitor before taking any action with regard to dose de-escalation.

Subjects who demonstrate disease flare after dose de-escalation have the opportunity to re-escalate their dose back to adalimumab ew dosing prior to Amendment 4 or to the next higher dose after Amendment 4. The investigator should receive prior approval from the medical monitor before taking any action with regard to dose re-escalation. One de-escalation within a period of 48 weeks and one re-escalation within a period of 48 weeks are permissible.

No study drug will be administered or injected at the final visit.

Subjects may discontinue adalimumab treatment at any time during study participation. Subjects that end study participation early will have a Termination Visit. All subjects will have a follow-up phone call approximately 70 days after the last administration of study drug to obtain information on any new or ongoing AEs.

[figure not shown]
An Example of 70-Day Follow-Up Call – Form is described in Appendix G.

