6.0 Analysis Conventions

General Considerations

All statistical analysis results will be reported using descriptive statistics. Descriptive summary statistics will be provided for the demographic and Baseline characteristics, efficacy, and safety parameters.

Continuous variables will be summarized by sample size (N), mean, standard deviation, minimum, Q1, median, Q3, and maximum. Frequency and percentages will be provided for the categorical variables. For dichotomized efficacy variables, data will be summarized by number and percent of subjects with 95% confidence interval.

Week 0 and Baseline Visit Date

Week 0 is defined as the Week 52 visit from the Study M11-290. This date is also referred to as the baseline visit date.

Definition of Baseline Measurement

Unless otherwise notes, the baseline value for a variable is defined as the last non-missing value before the baseline visit date (i.e., at or before the Week 52 visit from the Study M11-290). In some instances Study M11-290-Baseline will be used, but this will always be specified accordingly.

[figure not shown]
Definition of Final Measurement

Final evaluation during the study: the last non-missing observation collected in the study after the first dose of study drug.

Final evaluation during ADA exposure in Study M10-870 (for laboratory analyses): the last non-missing observation collected in the study within the ADA exposure window in Study M10-870 (see Section 9.1).

Definition of Rx Days (Days Relative to the First Dose of Study Drug)

Rx Days are calculated for each time point relative to the date of first dose of study drug in Study M10-870. They are defined as the number of days between the day of the first dose of study drug and the specific time point. Rx Days are negative values when the time point of interest is prior to the first study drug dose day. Rx Days are positive values when the time point of interest is after the first study drug dose day. The day of the first dose of study drug is defined as Rx Day 1, while the day prior to the first study drug dose is defined as Rx Day –1 (there is no Rx Day 0).

[figure not shown]

Definition of Analysis Windows

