9.0 Study Drug Exposure and Compliance

The duration (days) of study drug exposure and treatment compliance (%) will be summarized using descriptive statistics.

Study drug exposure will be calculated as follows:

ADA exposure in Study M10-870 = last dose date of ADA in Study M10-870 – first dose date of ADA in Study M10-870 + 14 days

Overall ADA exposure in Study M11-290 & Study M10-870 = ADA exposure in Study M10-870 + Overall ADA exposure in Study M11-290 (see Study M11-290 SAP)

Treatment compliance (%) is defined as the number of study drug injections received divided by the number of injections planned.

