11.2 Analysis of Adverse Events

Treatment emergent AEs, serious adverse events (SAEs), and AEs of special interest will be summarized.

AEs of special interest include:

- Infections
- Serious infections
- Opportunistic infections excluding oral candidiasis and tuberculosis (TB)
- TB (active/latent)
- Oral candidiasis
- Legionella infections
- Parasitic infections
- Diverticulitis
- Malignancies
- Lymphoma
- Hepatosplenic T-cell lymphoma (HSTCL)
- Leukemia
- Non-melanoma skin cancer (NMSC)
- Melanoma
- Malignancy other than lymphoma, HSTCL, leukemia, NMSC or melanoma
- Lupus-like reactions and systemic lupus erythematosus
- Allergic reactions including angioedema/anaphylaxis
- Stevens-Johnson syndrome
- Sarcoidosis
- Vasculitis (cutaneous/non-cutaneous)
- Demyelinating disorder
- Interstitial lung disease
- Congestive heart failure (CHF)
- Myocardial infarction (MI)

[figure not shown]

- Cerebrovascular accident (CVA)
- Intestinal perforation
- Pancreatitis
- Hematologic disorders including pancytopenia
- Liver failure and other liver events
- Reactivation of Hepatitis B
- Autoimmune Hepatitis
- Injection site reaction
- Erythema multiforme
- Worsening or new onset of psoriasis
- Pulmonary embolism
- Progressive multifocal leukoencephalopathy (PML)
- Reversible posterior leukoencephalopathy syndrome (RPLS)
- Amyotrophic lateral sclerosis
- Humira administration related medication error

Treatment-emergent AEs are defined as events with an onset date after the first dose of the study drug in Study M10-870 (i.e., on/after Rx Day 1) and with an onset date no more than 70 days after the last dose of the study drug in Study M10-870.

AEs with missing or unknown severity will be categorized as severe. AEs with missing or unknown relationship to study drug will be categorized as 'Reasonable Possibility' of being related to study drug. AEs that are reported more than 70 days after last dose of study drug will be excluded from the AE summaries; however, all reported AEs will be included in the AE data listings.

Overview tables of number and percentage of subjects with treatment-emergent AEs and events per 100 patient-years of ADA exposure in Study M10-870 (as defined in Section 9.0) will be provided.

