11.3 Analysis of Laboratory Data

Hematology	Clinical Chemistry	Urinalysis ^a
Hematocrit	Blood Urea Nitrogen (BUN)	Specific gravity
Hemoglobin	Creatinine	Ketones
Red Blood Cell (RBC) count	Total bilirubin	pН
White Blood Cell (WBC)	Albumin	Protein
count	Serum glutamic-pyruvic	Glucose
Neutrophils	transaminase	Blood
Bands	(SGPT/ALT)	Others
Lymphocytes	Serum glutamic-oxaloacetic	
Monocytes	transaminase	High-sensitivity C-reactive
Basophils	(SGOT/AST)	protein (hs-CRP)
Eosinophils	Alkaline phosphatase	β-HCG
Platelet count (estimate not	Sodium	
acceptable)	Potassium	
	Calcium	
	Inorganic phosphorus	
	Uric acid	
	Cholesterol	
	Total protein	
	Glucose	
	Triglycerides	

For selected continuous clinical laboratory parameters, change from baseline to minimum (smallest) value, maximum (largest) value, and final value during ADA exposure in Study M10-870 will be summarized using descriptive statistics.

[figure not shown]
A listing of all subjects with any clinical laboratory determinations during the study meeting criteria for potentially clinically importance (Common Toxicity Criteria [CTC] $Grade \geq 3$, based on the National Cancer Institute Common Toxicity Criteria for Adverse Event (NCI CTCAE) scale, most recent version) will be provided. For each of these subjects, the whole course of the parameter will be listed.

CTC Grading derived from NCI CTCAE v. 5.0

Test	Grade 1	Grade 2	Grade 3	Grade 4
Hemoglobin decreased	< LLN - 100 g/L	< 100 – 80 g/L	< 80 g/L	-
White blood cell decreased	$<$ LLN - 3.0 \times 10 9 /L	$< 3.0 - 2.0 \times 10^9/L$	$< 2.0 - 1.0 \times 10^9 / L$	$< 1.0 \times 10^9/L$
Neutrophil count decreased	< LLN - 1.5 × 10 ⁹ /L	< 1.5 - 1.0 × 10 ⁹ /L	< 1.0 - 0.5 × 10 ⁹ /L	$< 0.5 \times 10^9/L$
Lymphocyte count decreased	$<$ LLN - 0.8 \times 10 ⁹ /L	$< 0.8 - 0.5 \times 10^9 / L$	$< 0.5 - 0.2 \times 10^9 / L$	$< 0.2 \times 10^9 / L$
Platelet count decreased	$<$ LLN - 75.0 \times 10 9 /L	< 75.0 - 50.0 × 10 ⁹ /L	< 50.0 - 25.0 × 10 ⁹ /L	< 25.0 × 10 ⁹ /L
Creatinine increased	> ULN - 1.5 × ULN	> 1.5 - 3.0 × baseline; > 1.5 - 3.0 × ULN	> 3.0 × baseline; > 3.0 - 6.0 × ULN	> 6.0 × ULN
Bilirubin increased	> ULN - 1.5 × ULN if baseline was normal; > 1.0 - 1.5 × baseline if baseline was abnormal	> 1.5 - 3.0 × ULN if baseline was normal; > 1.5 - 3.0 × baseline if baseline was abnormal	> 3.0 - 10.0 × ULN if baseline was normal; > 3.0 - 10.0 × baseline if baseline was abnormal	> 10.0 × ULN if baseline was normal; > 10.0 × baseline if baseline was abnormal

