11.4 Analysis of Vital Signs and Weight

The following vital sign parameters will be obtained at each visit and summarized:

- Sitting systolic blood pressure (mmHg)
- Sitting diastolic blood pressure (mmHg)
- Sitting heart rate (or pulse) (bpm)
- Weight (kg)
- Height (cm)
- Body Mass Index (kg/m²)
- Respiratory rate (rpm)
- Body temperature (°C)

For continuous vital sign parameters, mean change from Baseline to minimum (smallest) value, maximum (largest) value, and final value during ADA exposure in Study M10-870 will be summarized. Subjects with potentially clinically significant results during ADA exposure in Study M10-870 will be identified according to the criteria in Table 3. Vital sign results meeting the criteria for potentially clinically significant findings will also be identified in a listing.

[figure not shown]

Table 3. Criteria for Potentially Clinically Significant Vital Sign Results

[figure not shown]
Vital Sign	Criterion	Definition of Potentially Clinically Significant
Systolic blood pressure	Low	Value ≤ 70 mmHg and decreased ≥ 20 mmHg from initial value
	High	Value $\geq 160 \text{ mmHg}$ and increased $\geq 20 \text{ mmHg}$ from initial value
Diastolic blood pressure	Low	Value \leq 50 mmHg and decreased \geq 15 mmHg from initial value
	High	Value ≥ 105 mmHg and increased ≥ 15 mmHg from initial value
Pulse	Low	Value \leq 50 bpm and decreased \geq 30 bpm from initial value
	High	Value ≥ 120 bpm and increased ≥ 30 bpm from initial value

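### The SAP does not define where the laboratory and vital-sign exposure window ends, and the final visit of an every-other-week subject falls on that undefined edge

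*SAP*

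**What the plan says.** SAP Section 6.0 (Definition of Final Measurement) separates a final evaluation during the study from a final evaluation during adalimumab exposure. The second, meant for laboratory analyses, is "the last non-missing observation collected in the study within the ADA exposure window in Study M10-870 (see Section 9.1". Section 9.0 has no subsections and is followed by Section 10.0. Its exposure rule is a length of time: "last dose date of ADA in Study M10-870 – first dose date of ADA in Study M10-870 + 14 days".

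Two sections use the restriction:

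- Section 11.3 summarizes change from baseline to minimum, maximum and "final value during ADA exposure in Study M10-870 will be summarized using descriptive statistics".
- Section 11.4 limits the same three vital-sign summaries to exposure, and adds: "Subjects with potentially clinically significant results during ADA exposure in Study M10-870 will be identified according to the criteria in Table 3".

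Protocol Section 5.1 states: "No study drug will be administered or injected at the final visit". For adverse events, SAP Section 11.2 uses a longer window and counts events "with an onset date no more than 70 days after the last dose of the study drug in Study M10-870".

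**The concern.** The exposure restriction decides which values enter the main laboratory and vital-sign change summaries, yet a programmer cannot find its end day in the SAP. The only available rule adds 14 days to the last dose, and 14 days is also the nominal gap between the last eow dose and the final visit. Whether that visit counts therefore depends on how the boundary is read and on a day or two of scheduling, not on safety.

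Long-term safety is a stated objective and about 55 subjects are expected outside Japan. If the last visit is left out, an abnormal value there cannot become the minimum, maximum or final value, and an abnormal vital sign that day is not flagged. An adverse event with onset on the same day is still counted.

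**Working it through.** **Inputs**

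- Day numbering: "The day of the first dose of study drug is defined as Rx Day 1", with no Day 0 (SAP 6.0).
- Week 288 nominal day: 2017 (SAP 6.0, analysis windows).
- Dosing dates run from Baseline, with ±3 days allowed (Protocol 5.3.1.1, Study Drug Dispensing/Administration).
- Visits also have ±3 days (Protocol 5.1 and Table 1).
- No dose at the final visit (Protocol 5.1).
- After premature discontinuation, termination procedures are due within 2 weeks of the last dose (Protocol 5.4.1).
- At study conclusion, the termination visit replaces a regular visit (Protocol 5.4.2).

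**1. Reproduce the SAP's nominal day.** Nominal day = 7 × week + 1. For Week 288: 7 × 288 + 1 = 2017, as stated. The formula matches all 20 rows of the SAP table.

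**2. Last eow dose.** It is due at Week 286: 7 × 286 + 1 = Rx Day 2003. The gap to Week 288 is 2017 − 2003 = 14 days. All scheduled clinic visits fall on even weeks, so a termination visit that replaces a regular one has the same 14-day gap.

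**3. Exposure duration.** 2003 − 1 + 14 = 2016 days. There are two ways to turn this into a window:

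- Reading A, through last dose + 14 days inclusive: ends on 2003 + 14 = Rx Day 2017. The visit is the last day inside.
- Reading B, 2016 days counted from Rx Day 1: ends on Rx Day 2016, which is last dose + 13. The visit is one day outside.

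**4. Allowed shifts.** With visit shift v and dose shift d, the gap is 14 + v − d. For an on-time last dose (d = 0) and a visit 1 to 3 days late, the gap is 15 to 17 days, which is outside under both readings.

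| Case | Inside, reading A | Inside, reading B |
|---|---|---|
| Eow, dose on time, visit ±3 days | 4 of 7 | 3 of 7 |
| Eow, dose and visit each ±3 days | 28 of 49 | 21 of 49 |
| Weekly (last dose Week 287, Rx Day 2010, gap 7), each ±3 days | 49 of 49 | 49 of 49 |
| Premature discontinuation, visit 0 to 14 days after last dose | 15 of 15 | 14 of 15 |

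These are counts of calendar combinations, not expected frequencies. If all 49 eow combinations were equally likely, 21/49 = 43% (A) or 28/49 = 57% (B) of final visits would be outside. Now assume instead that each shift is zero with probability 0.70 and takes each other value with probability 0.05. Then P(v = d) = 0.70² + 6 × 0.05² = 0.505. The share outside is (1 − 0.505)/2 ≈ 25% under A, and 0.505 + 0.2475 ≈ 75% under B. The result depends on the assumed distribution and the reading, and the documents give neither.

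**5. What replaces an excluded value.** The visit before Week 288 is Week 264, Rx Day 1849: 2017 − 1849 = 168 days = 24 weeks. The same spacing holds for any final visit after Week 120, unless there was an unscheduled visit in between.

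**The case against.** A reader might infer that the window always closes before the final visit, so that end-of-treatment values disappear from the safety reporting. The documents do not support this, for four reasons.

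- If the window runs through last dose + 14 days, an on-schedule Week 288 visit is inside, on its last day. The one-day miss needs reading B, which the SAP does not state.
- Weekly dosing leaves a 7-day gap. A premature-discontinuation visit held within the required 2 weeks is inside reading A, and reading B excludes only day 14.
- Much of the laboratory output keeps the final visit. The Grade 3 or higher listing covers the whole study. The CTC shift tables and the liver listing state no exposure limit (SAP 11.3). Albumin, total protein, hemoglobin, hematocrit, red cell count and hs-CRP are summarized over time (SAP 10.2), with a Week 288 window of Rx Days 1934 to 2101.
- A shorter on-treatment window for laboratory values than for adverse events is a legitimate choice. SAP 7.3 also uses last dose + 14 days for concomitant medication. A +70-day window could admit values taken after another therapy has begun, because Protocol 5.4.1 only prefers that the termination visit come first.

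All four stand, and they narrow the point. They do not remove it: the end day is still undefined, and an eow final visit 1 to 3 days late after an on-time last dose is excluded on either reading although it complies with the protocol. A subject who stops for good during a long pause can also be outside. Protocol 6.3, for example, implies at least 2 + 2 weeks without injections around elective surgery.

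**Conclusion.** The point holds in limited form. The cross-reference is dead, the window has no stated end, and the eow final visit sits exactly on the likely boundary. The loss is confined to the minimum, maximum and final change summaries for laboratory values and vital signs, and to the flagging of potentially clinically significant vital signs. Where a final visit is excluded after Week 120, the reported final value can be about 24 weeks older.

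The share of final visits affected cannot be derived. A reader might take 43% to 57% as an estimate, but that range holds only for uniform, independent shifts over ±3 days. The protocol instead asks for a fixed dosing weekday and for effort to bring subjects back to schedule. The share of subjects on eow dosing at their final visit is not given either. The SAP is written to Amendment 3, which still allowed weekly dosing, whereas the protocol synopsis puts all subjects on eow dosing after Amendment 4.

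This is more than missing detail, because two programmers following the SAP could produce different tables and because visits that comply with the protocol are excluded on both readings.

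**What to change.** In SAP 6.0, 11.3 and 11.4:

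- Replace the reference to Section 9.1 with an explicit definition: the exposure window runs from the first dose in Study M10-870 through the last dose date + 14 days, inclusive. Apply it to vital signs as well as laboratory values.
- State that the Week 288 or premature-discontinuation (termination) visit is always included in the minimum, maximum, final and potentially-clinically-significant summaries, even if it falls a few days later.

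The cost is a few lines of SAP text and one programming rule. A few values taken more than 14 days after the last dose will be counted. For eow subjects within both ±3-day windows, the gap cannot exceed 14 + 3 + 3 = 20 days. Extending the whole window to +70 days to match adverse events is optional and not needed to correct this point.

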All time points and corresponding time windows are defined based on Rx days. The protocol specified visits and corresponding time windows are presented in the table below. Measures will only be displayed at the visits where they were planned to be measured. For example, Mayo score is collected at Weeks 0, 48, 96, 192 and 288/Premature Discontinuation (dependent on availability of optional endoscopy data at these timepoints).

Assigned Visit	Nominal Day	Time Window (Rx Day Range)
Week 0	1	≤ 1
Week 4	29	2 to 43
Week 8	57	44 to 71
Week 12	85	71 to 127
Week 24	169	128 to 211
Week 36	253	212 to 295
Week 48	337	296 to 379
Week 60	421	380 to 463
Week 72	505	464 to 547
Week 84	589	548 to 631
Week 96	673	632 to 715
Week 108	757	716 to 799
Week 120	841	800 to 925
Week 144	1009	926 to 1093
Week 168	1177	1094 to 1261
Week 192	1345	1262 to 1429
Week 216	1513	1430 to 1597
Week 240	1681	1598 to 1765
Week 264	1849	1766 to 1933
Week 288	2017	1934 to 2101

If more than one assessment is included in a time window the assessment closest to the nominal day should be used. If there were more than one observation with equal distance to the nominal day the latest one will be used in analyses. For any given variable, if more

than one measurement exists for a subject on the same day, the average of the measurements will be considered to be that subject's measurement for that day.

Missing Data Handling

In general, missing Baseline and safety data will not be imputed.

Baseline Value is Missing:

Subjects will be excluded from analysis of change from Baseline if Baseline evaluation is missing.

Missing Efficacy and Outcome Evaluations:

The following methods will be used for imputing missing values to perform the efficacy analyses.

[figure not shown]
For interim analyses, missing values will only be imputed up to the timepoint a patient could have potentially reached at the data cutoff for analyses.

Observed Cases (OC): missing values will not be used for the observed case analysis.

Last Observation Carried Forward (LOCF): For categorical and continuous efficacy variables the following rules will be used for LOCF approach:

- Baseline and pre-baseline values will not be used to impute the missing post-baseline values, and
- Missing values after baseline will be imputed using the last non-missing values after baseline and prior to the missing value.

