SGPT/ALT increased	> ULN - 3.0 × ULN if baseline was normal; 1.5 - 3.0 × baseline if baseline was abnormal	> 3.0 - 5.0 × ULN if baseline was normal; > 3.0 - 5.0 × baseline if baseline was abnormal	> 5.0 - 20.0 × ULN if baseline was normal; > 5.0 - 20.0 × baseline if baseline was abnormal	> 20.0 × ULN if baseline was normal; > 20.0 × baseline if baseline was abnormal
SGOT/AST increased	> ULN - 3.0 × ULN if baseline was normal; 1.5 - 3.0 × baseline if baseline was abnormal	> 3.0 - 5.0 × ULN if baseline was normal; > 3.0 - 5.0 × baseline if baseline was abnormal	> 5.0 - 20.0 × ULN if baseline was normal; > 5.0 - 20.0 × baseline if baseline was abnormal	> 20.0 × ULN if baseline was normal; > 20.0 × baseline if baseline was abnormal
Alkaline phosphatase increased	> ULN - 2.5 × ULN if baseline was normal; 2.0 - 2.5 × baseline if baseline was abnormal	> 2.5 - 5.0 × ULN if baseline was normal; > 2.5 - 5.0 × baseline if baseline was abnormal	> 5.0 - 20.0 × ULN if baseline was normal; > 5.0 - 20.0 × baseline if baseline was abnormal	> 20.0 × ULN if baseline was normal; > 20.0 × baseline if baseline was abnormal

Shift tables from baseline to worst CTC grade will be provided.

The liver-specific laboratory tests include the serum glutamic pyruvic transaminase (SGPT/ALT), serum glutamic-oxaloacetic transaminase (SGOT/AST), alkaline phosphatase, and total bilirubin. A listing of potentially clinically significant liver function laboratory values will be provided. The listing will include all subjects who met any of the following 4 criteria:

- ALT $\geq 3.0 \times ULN$, or
- AST \geq 3.0 × ULN, or
- Alkaline phosphatase $\geq 1.5 \times ULN$, or
- Total bilirubin $\geq 2.0 \times ULN$.

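### Same-day averaging in SAP 6.0 has no safety exception, so it can soften post-baseline laboratory and vital-sign extremes, and it is not reconciled with the Grade 3 or higher listing

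*SAP*

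**What the plan says.** The same-day rule closes the analysis-windows part of SAP 6.0. It begins "For any given variable, if more" than one measurement falls on one day, and ends by saying that "the average of the measurements will be considered to be that subject's measurement for that day". Safety data are not excepted.

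SAP 11.3 then asks for four laboratory outputs that depend on extreme values:

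- for selected continuous parameters, "change from baseline to minimum (smallest) value, maximum (largest) value, and final value during ADA exposure" in this study;
- a listing at CTC Grade 3 or higher, defined as "A listing of all subjects with any clinical laboratory determinations during the study" that meet the criterion, with the addition that "For each of these subjects, the whole course of the parameter will be listed";
- "Shift tables from baseline to worst CTC grade will be provided";
- a liver listing of subjects who reach any of four multiples of the ULN.

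SAP 11.4 has the same structure for vital signs: change to minimum and maximum, and the threshold criteria of Table 3. Apart from the word *any* in the Grade 3 or higher listing, nothing in 11.3 or 11.4 says whether individual results or daily values are used.

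**The concern.** Averaging suits a by-visit mean, but not a table meant to show the worst value a subject had. The mean of two post-baseline results is never more extreme than the worse of them. It can pull a maximum down, a minimum up, and a result back across a grade or threshold boundary.

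Long-term safety is the first-named objective (SAP 4.1), all results are descriptive (SAP 6.0), and about 55 subjects are expected outside Japan (SAP 4.3). In a study of that size a single Grade 3 value is visible in a table, and so is its absence. Two outputs could also disagree about the same child: the listing, if built on individual determinations, would show a Grade 3 value that the shift table, if built on daily means, would not.

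**Working it through.** The plan gives no figure to reproduce and the documents contain no subject data. The check applies the SAP 6.0 rule to assumed pairs of same-day post-baseline results and grades them with the cut-offs in SAP 11.3.

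**Cut-offs.** ALT with normal baseline: Grade 2 is "> 3.0 - 5.0 × ULN if baseline was normal" and Grade 3 is "> 5.0 - 20.0 × ULN if baseline was normal". The Grade 2/3 boundaries for low counts are neutrophils 1.0, lymphocytes 0.5 and platelets 50 (all x 10^9/L), and hemoglobin 80 g/L.

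**Pairs that change grade.** Daily value = (a + b)/2.

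| Test | Pair | Mean | Worst individual grade | Grade of mean |
|---|---|---|---|---|
| ALT (x ULN) | 5.4, 3.6 | 4.5 | 3 | 2 |
| Neutrophils | 0.9, 1.3 | 1.1 | 3 | 2 |
| Lymphocytes | 0.45, 0.60 | 0.525 | 3 | 2 |
| Platelets | 48, 60 | 54 | 3 | 2 |
| Hemoglobin (g/L) | 78, 84 | 81 | 3 | 2 |

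**Pairs that do not.** ALT 6.0 and 4.5 gives 5.25, ALT 12 and 1 gives 6.5, neutrophils 0.8 and 1.1 gives 0.95, and hemoglobin 75 and 83 gives 79. All stay Grade 3.

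**When ALT is downgraded.** With a first value a above 5 x ULN, (a + b)/2 <= 5 requires b <= 10 - a. For a = 5.5 the second value must be 4.5 or less; for a = 8 it must be 2 or less. Once a reaches 10, no positive second value brings the mean out of Grade 3.

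**Threshold criteria.** The liver listing takes ALT at or above 3.0 x ULN. Results of 3.2 and 2.6 average 2.9, which misses it. For total bilirubin (at or above 2.0 x ULN), 2.1 and 1.7 average 1.9, which also misses. For an upper limit T, two results fall below it on average when b < 2T - a. For the systolic limit of 160 mmHg in Table 3, that is b < 320 - a.

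**Baseline behaves differently.** SAP 11.3 grades ALT, AST, alkaline phosphatase and bilirubin by whether baseline was normal. Take baseline ALT results of 1.2 and 0.6 x ULN and a later value of 5.5 x ULN:

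- averaged baseline: (1.2 + 0.6)/2 = 0.9, normal, so 5.5 x ULN is Grade 3;
- worse baseline result: 1.2, abnormal, so 5.5/1.2 = 4.6 x baseline, Grade 2.

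Taking the worst value of the day at baseline could therefore itself lower a later grade.

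**Size per subject.** 1/55 = 1.8%.

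**The case against.** The best defence is placement. The sentence follows the rules that choose one value per visit window, while the SAP 11.3 minimum, maximum and final values are taken over the exposure period and not by window. The authors may have meant it for by-visit summaries only. That intention is plausible, but the text does not state it. The rule covers any variable and defines the value for a day, not for a visit. SAP 6.0 as a whole covers safety: it defines a final evaluation for laboratory analyses and, just after the averaging rule, treats safety data separately for imputation. No such separation is made here.

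Four stronger readings are tempting, and the documents do not support them:

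- *A Grade 3 value drops out of the Grade 3 or higher listing.* That listing has its own selection rule, based on any determination. Read plainly, it keeps the value. The most that can be said is that the two rules are not reconciled, because a programmer could average first.
- *Local and central samples on one day will trigger the rule.* Protocol 5.3.1.1 makes local testing a substitute when site sampling is prevented. It describes no parallel draw.
- *The rule always works in the favourable direction.* That holds for post-baseline extremes, but not for baseline-dependent grades, as shown above.
- *Serious abnormalities would go unseen.* Clinically significant results are followed to resolution (Protocol 5.3.1.1). Abnormalities that lead to discontinuation, need intervention or are judged adverse events by the investigator are reported as such (Protocol 6.1.2). Averaging touches neither route.

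It also stands that Protocol Table 1 schedules no same-day repeats, and that the pairs in the upper table were chosen to cross a cut-off.

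**Conclusion.** The rule is wrong as written for post-baseline safety extremes. It is a stated rule that gives the wrong answer there, not merely a missing detail. It can soften the minimum and maximum summaries, the worst CTC grade in the shift table, and the liver and vital-sign threshold criteria. It is also unreconciled with the any-determination wording of the Grade 3 or higher listing.

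The practical importance is low. With no same-day pairs the effect is nil, and each child reclassified moves a percentage by 1.8 points on 55 subjects. The number of such pairs is not given and is probably low, and a downgrade needs the mean to cross a cut-off. The conclusion assumes that the averaging rule is programmed literally and before the safety outputs are derived.

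**What to change.** In SAP 6.0, limit same-day averaging to the baseline value and by-visit summaries. In SAP 11.3 and 11.4, state that post-baseline minimum, maximum, worst CTC grade, liver criteria, vital-sign criteria and all safety listings use every individual determination. Keep the individual-result rule to post-baseline data, for the reason shown in the baseline example. Say also which rule the final value follows; it is not an extreme, so either choice works if it is stated.

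The cost is a sentence or two before programming, with no new data. The downside is that reported post-baseline grades may be slightly less favourable. A count of subject-days with more than one result for the same test would show whether any table is affected.
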